The aim of this study is to determine the onset time, duration of action and effect on intubating conditions for rocuronium 0.6 mg/kg in patients aged 18-40 years and in patients with age > 80 years. The hypothesis of this study is that rocuronium administered in elderly patients (>80 years) has a longer onset in the elderly compared to younger patients.

Method:

Design:

Observational clinical study

Outcomes:

The primary end point is onset time, defined as the time from the end of rocuronium injection to Train-of-four (TOF) count of 0 monitored by acceleromyography.

The secondary endpoints are intubating conditions rated by an intubating difficulty scale¹¹ after 90 seconds and duration of action, defined as time from end of rocuronium injection to reappearance of TOF ratio > 0.9.

The pharmacodynamic data obtained are: time to reappearance of the T1, time to T1 recovery to 25% (of the final T1), and time to T0F ratio 0.90

Number of patients: 32 patients (16 in each group):

Group young: 16 patients receiving rocuronium 0.6 mg/kg

Group elderly: 16 patients receiving rocuronium 0.6 mg/kg

Doses are based on ideal body weight, calculated as height (cm) minus 105 for women and height (cm) minus 100 for men.

Inclusion criteria:

Patients > 18 years old

Informed consent

Scheduled for elective surgery (>1 hour) under general anaesthesia with intubation and use of rocuronium

3

American Society of Anesthesiologists (ASA) physical status classification I to III
Can read and understand Danish
Exclusion criteria:
Known allergy to rocuronium
Neuromuscular disease that may interfere with neuromuscular data
Indication for rapid sequence induction
End of study:
When 32 patients have been evaluated considering the primary endpoint the study is concluded
Pre-operative assessment:
In the Case Report Form (CRF) the following baseline data is noted:
Age
Sex
Weight
Height
BMI
ASA group (I-IV)
Co-morbidity

Perioperative treatment:

Monitoring:

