The patient will be monitored with ECG, noninvasive blood pressure, oxygen saturation, and temperature sensors in nose cavity or bladder. Neuromuscular monitoring will be performed with TOF-Watch SX connected to a computer for collection of neuromuscular data (Version 2.5 INT 2007, Organon, The Netherlands). The monitoring will be done according to international guidelines¹³. TOF-Watch SX will be placed on the arm, where there is the least monitoring in general. Initially, the skin will be shaved and cleansed and rubbed with an abrasive. Small ECG electrodes will be used. They will be placed on the wrist over the ulnar nerve. The acceleration transducer will be placed on the thumb and attached in the associated hand adaptor. When the patient is adequately anesthetized we will start the TOF Watch SX and give two train-of-four (TOF) nerve stimulations followed by a tetanic stimulation with 50 Hz for 5 seconds. Then we will calibrate the TOF Watch SX with the CAL2 button and start the TOF mode and measure the TOF (2 Hz for 1.5 seconds) each 15 sec. After securing a stable signal with less than 5% deviation for two minutes we will inject rocuronium. When TOF = 0 we will measure the PTC for every 3-4 minutes.

An intravenous catheter will be placed in the opposite hand.

Anesthesia:

General anesthesia comprises induction with propofol 1-2 mg/kg and fentanyl 1.5-3.0 mcg/kg. Tracheal intubation is performed 90 seconds after administration of rocuronium 0.6 mg/kg. Anesthesia will be maintained with propofol approximately 5 mg/kg/hour and remifentanil 0.25-0.5 mcg/kg/min and adjusted according to depth of anesthesia.

Treatment values:

Blood pressure: Mean arterial pressure (MAP) max. 30 % difference from baseline.

Neuromuscular monitoring continues until TOF \geq 0.90 and stable over 2 min. In case of TOF < 0.90 at the end of surgery the NMB is reversed with neostigmine or sugammadex according to guidelines at the department. Subsequently, the patient is awakened and taken to the recovery room.

Intubating conditions:

Intubating conditions will be assessed 90 seconds after end of injection of rocuronium 0.6 mg/kg employing the Intubating Difficulty Scale. The scale comprises seven items:

N1-The number of supplementary attempts, an attempt defined as one advancement of the tube in the direction of the glottis during direct laryngoscopy or one like advancement of the tube in the case of a blind intubation trial.

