N2-The number of supplementary operators; N2represents the number of additional persons directly attempting (i.e., not assisting) intubation.

N3-The number of alternative techniques used. For example, changing from an oral intubation to blind nasotracheal intubation or from a curved blade to straight blade increases N3by 1 point. The various techniques used should be noted in chronological order, so that subsequent identification of techniques ineffective in a particular case (or series) may be undertaken.

N4-Glottic exposure as defined by the Cormack grade [4] minus one; grade I (N4= 0) on this scale corresponds to complete visualization of the vocal cords, grade II (N4= 1) to visualization of the inferior portion of the glottis, grade III (N4= 2) to visualization of only the epiglottis, and grade IV (N4= 3) to a nonvisualized epiglottis. Glottic exposure is evaluated during the first attempt by the first operator. In case of successful intubation after blind nasotracheal intubation, N4= 0. If the blind attempt(s) fail, glottic exposure is evaluated during the first subsequent alternative visualized laryngoscopic attempt.

N5-The lifting force applied during laryngoscopy; N5= 0 if little effort is necessary, and N5= 1 if subjectively increased lifting force is necessary. This notion is based on the operator's impression that an abnormal amount of force was used compared with routine practice.

N6-The necessity of applied external laryngeal pressure for optimized the glottic exposure; N6= 0 if no external pressure is applied. N6= 1 if external laryngeal pressure is necessary. Application of the Sellick Maneuver is intended to inhibit aspiration of gastric contents and does not alter the score.

N7-Position of vocal cords; N7= 0 if vocal cords are in abduction. N7= 1 if the vocal cords are in abduction, presenting an impediment to tube passage. If the vocal cords are not visualized, N7= 0 by default.

Positioning:

The patient will be positioned with the arm with neuromuscular monitoring equipment in abducted position. It is ensured that the monitoring equipment is as unaffected as possible to achieve the most precise neuromuscular data. Intravenous cannula will be placed in opposite hand than neuromuscular monitoring equipment.

Surgery:

Surgery with use of rocuronium 0.6 mg/kg for intubation.

Respiratory:

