Patients are oxygenated at FiO2=1.0 during preoxygenation and induction of anesthesia until the trachea is intubated. Anesthesia continues initially with FiO2=0.30. Patients are ventilated with Pressure Control Ventilation, tidal volume 7 ml/kg, PEEP (positive end-expiratory pressure) 5 cm H2O and respiration frequency 10-12 targeting normocapnia (ETCO2 at 4.5-5.5 kPa). If PaCO2> 6 kPa primarily the respiration frequency (RF) will be increased. If hypoxemia arises, defined as SpO2< 95 or PaO2< 10 kPa primarily FiO2 will be increased. In the event of deficient effect, PEEP will be increased.

Fluid therapy:

1000 ml Ringer lactate is given intraoperatively. Blood loss up to 500 ml is replaced with Ringer lactate 1:2.5. Blood loss in excess of this is replaced in accordance with the local guidelines.

In case of hypotension ephedrine or phenylephrine will be administered. In case of need for continuous inotropic infusion phenylephrine or noradrenalin will be used.

Antibiotics:

According to local guidelines. Dose and name will be noted on the CRF.

Pain treatment:

Postoperative pain treatment with paracetamol, fentanyl, morphine and peripheral nerve blocks according to local guidelines.

PONV treatment:

PONV prophylaxis and treatment with ondansetron, dexamethasone and droperidol according to local guidelines.

Data collection

Perioperative data collection that will be noted in CRF:

Type of operation with operation code

TOF values (NMB sheet)

Body temperature measured immediately after intubation and again immediately before extubation

Intubating difficulty score

Operating time (from incision to last suture)

Statistics:

Normal distributed variables will be expressed by means and standard deviations; variables that

are not normal distributed will be expressed by medians and interquartile ranges. Student's t-test

is used to compare normal distributed data and Mann-Whitney test to compare not normal

distributed data.

X2-test or Fisher's exact test will be used for frequencies when comparing the two groups.

Sample size:

We estimated a 20 seconds standard deviation for onset time of rocuronium based on previous

studies¹². We considered a difference in onset time of 30 seconds between the younger and

elderly groups to be clinically relevant. We have calculated that a sample size of 16 patients in

each group will allow us to detect this difference, with 5% Type 1 error risk and 90% power.

Schedule:

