Inclusion of 2-3 patients per week is expected corresponding to duration of inclusion of

approximately 10-16 weeks. Inclusion: Planned to go on in the period from December 2018 to

April 2019. Inclusion of patients will be stopped when the desired number of patients is achieved.

The trial will be counted as concluded, when the last patient has registered with the primary

endpoint.

Data analysis and reporting: from April 2019 to June 2019.

Risks and side effects

Rocuronium: According to the product summary side effects are:

Not common (0,1-1%): Hypotension, anafylactic reaction.

Seldom (< 0,01%): Shock, angioedema, face edema.

9

Tracheal intubation with use of rocuronium is routinely performed at Department of Anaesthesia, Centre of Head and Orthopedics, 4031 Rigshospitalet. In both groups the patients will receive rocuronium in a dose aiming to provide optimal intubating conditions. It is not regarded as a disadvantage to use rocuronium, since the effect is monitored through surgery and if needed fully reversed by a reversal agent upon end of surgery.

Ethical considerations:

Tracheal intubation is as a standard performed with use of a rocuronium 0.6 mg/kg. Anesthesia and surgery will follow standard guidelines. The possible benefit in this trial is to investigate whether rocuronium 0.6 mg/kg has a different onset time in the elderly compared to younger patients. This may result in different intubating difficulty scores between younger and elderly patients. The results may help to detect the optimal dose of rocuronium for intubation of the trachea in elderly patients.

Consent and patient recruitment:

Patients are recruited among those referred to the Department of Anaesthesia, Centre of Head and Orthopedics, 4031 Rigshospitalet who meet inclusion criteria and who have no exclusion criteria.

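### Item N7 of the Intubating Difficulty Scale, part of a secondary endpoint, gives the same cord position (abduction) for score 0 and score 1

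*Combined protocol and SAP*

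**What the plan says.** The Outcomes section makes the scale part of the endpoint set: "The secondary endpoints are intubating conditions rated by an intubating difficulty scale". The section on intubating conditions fixes the time and the instrument: "Intubating conditions will be assessed 90 seconds after end of injection of rocuronium 0.6 mg/kg employing the Intubating Difficulty Scale". It then lists the items, N1 to N7 ("The scale comprises seven items").

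The last item, N7, concerns the position of the vocal cords. Its scoring rule reads: "N7= 0 if vocal cords are in abduction. N7= 1 if the vocal cords are in abduction, presenting an impediment to tube passage". One further rule follows: "If the vocal cords are not visualized, N7= 0 by default".

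The Data collection section lists what goes on the case report form, and for this endpoint the entry is "Intubating difficulty score". Under Ethical considerations, after raising the possibility that onset time differs with age, the plan adds: "This may result in different intubating difficulty scores between younger and elderly patients".

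**The concern.** An item that records cord position needs a different position for each level, and here both levels name abduction. The only difference in the text is the added clause about obstruction to the tube, which sits oddly with cords that are open.

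This sentence is the rule by which a secondary endpoint is scored, in a study that expects the score may differ between its two groups. Cord position is one place where an incomplete block at 90 seconds could show. If a rater gives 0 to adducted cords because no written score covers them, the error occurs only in patients whose cords are adducted. Under the study's hypothesis of a longer onset in the elderly, such patients could be more common in that group, and the error would then shrink a real difference. This is a possible mechanism; the documents give no frequencies that would show how often it might occur.

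**Working it through.** **Step 1. Apply the written rule to each possible finding.** The inputs are the two N7 levels and the default rule, all from the section on intubating conditions.

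| Finding at laryngoscopy | Fits score 0 as written? | Fits score 1 as written? | Result |
|---|---|---|---|
| Cords seen, abducted, not obstructing | Yes | No | 0 |
| Cords seen, abducted, obstructing | Yes | Yes | Two scores apply |
| Cords seen, adducted | No | No | No score applies |
| Cords not seen | By default | No | 0 |

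If score 1 is read as adduction, the third row becomes 1 and the gap closes. The second row also stops being a conflict, because abduction then belongs to score 0 alone.

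**Step 2. Look for a correction elsewhere.** The Outcomes, Data collection, Statistics and Ethical considerations sections refer to the scale, to its score or to tests that could be applied to it. None of them defines N7. The default rule concerns unseen cords only, so it does not reach the third row.

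**Step 3. Bound the effect.** The plan states no figure on this point, so there is none to reproduce. Inputs:

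- 16 patients per group (Number of patients).
- N7 takes the value 0 or 1, so a misreading changes it by at most 1 point.
- Assumption: the recorded score is the sum of the seven items. The plan does not spell this out.
- Assumption: k patients in a group are misscored, all in the same direction. The documents give no value for k, so a range is shown.

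Largest shift in a group's mean score = k × 1 / 16.

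| k | Shift in group mean (points) |
|---|---|
| 1 | 1/16 = 0.0625 |
| 2 | 2/16 = 0.125 |
| 4 | 4/16 = 0.25 |
| 8 | 8/16 = 0.5 |
| 16 | 16/16 = 1.0 |

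If the errors go the same way in both groups, the difference in means changes by at most (k in the elderly − k in the young) / 16 in absolute size. It is 0 when k is equal. With k = 4 in the elderly and k = 1 in the young, it is 3/16 = 0.1875 points.

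These are arithmetic limits on means, not estimates. The Statistics section allows a t-test, a Mann-Whitney test, or a chi-square or Fisher test, and does not say which applies to this score. Under a rank or category comparison the k/16 figures do not describe the test result, and equal k need not leave it unchanged.

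**Step 4. Check what else depends on N7.** The primary endpoint is the interval from the end of injection to a TOF count of 0. The sample size rests on the standard deviation and difference assumed for that interval. Neither uses N7.

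**The case against.** The strongest reply is that this is a recoverable one-word slip. Score 1 carries the obstruction clause and score 0 does not, so a rater can score on obstruction and get the intended answer. The scale is also cited to a published source (reference 11), which gives raters a definition outside this sentence. This stands, and it is why the point is minor. It does not make the written rule correct, and no other text in the plan supplies the right one.

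A second reply is that the fault may lie in the reading of the PDF. *Abduction* and *adduction* differ by one letter, and a misread letter would still give a real word. The text has other character-level faults, such as a zero for the letter O in one mention of the TOF ratio under Outcomes. An artefact seems unlikely, since the sentence is complete running prose, but it is not excluded. Any correction should therefore wait for a look at the source PDF.

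A third reply is that nothing supports a k above 0, and that k = 16 would require every patient in a group to be misscored. That is right: the table gives limits only.

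Finally, the case report form has not been seen. If it holds only the total, a misread N7 could not be found later. The plan does not say so, however, and N3 asks for the techniques to be noted in order, which suggests that some detail below the total is kept. Loss of traceability is a possibility and has not been shown.

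**Conclusion.** The concern holds, as a minor point. As written, N7 uses one cord position for both of its levels, leaves visible adducted cords without a score, and is not corrected anywhere else in the document. That conclusion needs only the text, provided that the PDF carries the same word.

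The effect is at most 1 point per patient and at most k/16 points on a group mean, assuming that the score is the sum of the items. The number misscored cannot be estimated from the documents and may be 0. That adduction was intended is an inference from the obstruction clause and from the need for the two levels to differ; the cited scale was not available to confirm it.

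**What to change.** Check the N7 sentence in the source PDF and in the scale paper cited as reference 11. If both bear out the reading above, replace *abduction* with *adduction* in the definition of score 1 and leave the rest of the item as it is. Make the same change on the case report form or its scoring sheet if the wording was copied there.

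The cost is one word in the protocol and possibly one on the form. The sample size and the analysis do not change.
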